23. Active viral hepatitis (B or C) as demonstrated by positive serology at Screening
24. Psychotic disorder(s) or unstable recurrent affective disorder(s) evident by use of antipsychotics or prior suicide attempt(s) within approximately the last 2 years
25. History of drug or alcohol dependency or abuse within approximately the last 2 years; use of illegal recreational drugs
26. Concomitant use of medications known to be inducers of cytochrome P450 (CYP3A) including, but not limited to: rifampin, troglitazone, St John's Wort, efavirenz, nevirapine, glucocorticoids (other than topical usage), modafinil, pioglitazone, and rifabutin
27. Use of AEDs not recommended by Epilepsy Treatment Guidelines for use in LGS including, but not limited to carbamazepine, gabapentin, oxcarbazepine, phenytoin, pregabalin, tiagabine, and vigabatrin (revised per Amendment 02)
28. Any suicidal ideation with intent with or without a plan within 6 months before Visit 2 (ie, answering "Yes" to questions 4 or 5 on the Suicidal Ideation section of the Columbia Suicide Severity Rating Scale [C-SSRS]) in subjects aged 8 and above. (revised per Amendment 02)
29. Subjects with rare hereditary problems of galactose intolerance, the Lapp lactase deficiency or glucose-galactose malabsorption. (revised per Amendment 04)

Study Treatments

Test drug: Perampanel

Dosing should occur orally once a day before bedtime.

Note: For Visit 5 and Visit 6, predose and early postdose (within 1 to 5 hours after dosing) PK samples are to be collected. For these visits, if due to infeasibility of PK sample collection before and after evening/bedtime dose administration, then the following steps are to be followed:

- Study drug administration **in the evening immediately before Visit 5 and Visit 6 should be withheld** (all other AEDs should be administered per the subject's usual AED regimen).
- During Visit 5 and Visit 6, collect predose PK sample. Then administer study drug on site, followed by early postdose PK sample collection (within 1 to 5 hours after dose administration).
- Bedtime dosing will resume in the evening on the day of Visit 5 and Visit 6.
- In these cases, dosing date and time of the previous 3 doses before each PK sampling visit will continued to be recorded.

(revised per Amendment 04)

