Perampanel will be supplied as 2-mg oral tablets and 0.5 mg/mL oral suspension. It is recommended that oral tablet be used for dosing subjects ≥ 12 years of age, and oral suspension for subjects < 12 years of age. However, the most appropriate formulation may be selected based on the subject's condition and at the discretion of the investigator. The same formulation should be used for a given subject throughout the course of the study.

Comparator Drug: Matching-placebo

Core Study: Subjects will start perampanel at a dose of 2 mg/day (or matching placebo). Thereafter, the dose will

be increased up to a maximum target dose of 8 mg/day (or matching placebo) according to individual subject tolerability and efficacy. Once titrated, all subjects will be kept at a stable dose for at least 2 weeks (to reach steady-state) before the start of the Maintenance Period. The dose of study drug during the Maintenance Period will be the last dose achieved at the end of the Titration Period. See the dosing table for the dosing schedule in the Titration Period. (revised per Amendment 04)

Dosage Schedule in E2007-G000-338 (Randomization Phase –Core Study)

| Randomization Phase/ Titration Period | Visit | All Subjects |
|---|---|--------------|
| Week 1 (starting dose) | Visit 2 | 2 mg/day |
| Week 2 | Visit 3 | 4 mg/day |
| Week 3 | - | 6 mg/day |
| Week 4 | Visit 4 | 6 mg/day |
| Week 5 ^a | - | 8 mg/day |
| Week 6 ^a | - | 8 mg/day |
| Randomization Phase/ Maintenance Period (Week 7/Visit 5)^b | Starts the Maintenance Period at the last dose achieved in the Titration Period | |

a: Subjects will remain on dose for at least 2 weeks before entering the Maintenance Period.

b: Dosing should occur orally once a day before bedtime, except on the evenings immediately before (and the evening on the day of) Visits 5 and 6. Study drug administration in the evening immediately before (and the evening on the day of) Visit 5 and Visit 6 **should be withheld** (all other AEDs should be administered per the subject's usual AED regimen). **Study drug will be given during Visit 5 and Visit 6 at the study site, after collection of pre-dose PK sample** (within 1 to 5 hours after dose administration). Bedtime dosing will resume in the evening on the day of Visit 5 and Visit 6. (revised per Amendment 04).

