9.1.2.2 Core Maintenance Period

During the 12-week Maintenance Period, subjects will continue treatment with the dose and formulation of test drug (perampanel) or placebo achieved during the Titration Period, taking the study drug once daily in blinded fashion. The Maintenance Period will begin with Visit 5, and subjects will continue treatment at the last dose (or matching placebo) achieved in the Titration Period. Study drug administration in the evening immediately before (and the evening on the day of) Visit 5 and Visit 6 should be withheld (all other AEDs should be administered per the subject's usual AED regimen). Study drug will be given during Visit 5 and Visit 6 at the study site (within 1 to 5 hours after dose administration). Bedtime dosing will resume in the evening on the day of Visit 5 and Visit 6. In these cases, dosing date and time of the previous 3 doses before each PK sampling visit will continued to be recorded. Parents or caregivers will complete seizure diaries throughout the Core Study; all seizure types will be collected. Subjects will continue to take their baseline anti-epileptic medications throughout the study. (revised per Amendment 04)

Dose adjustment during the Maintenance Period is not recommended; however, the investigator may down-titrate a subject's dose if, in his/her clinical judgment, the subject experiencing intolerable AE(s) that warrant(s) such an action. In general, more than one down-titration of a subject's dose will be discouraged; however, if the subject continues to present significant intolerable AE(s) and the investigator deems it is necessary, the dose may be reduced further. During the Maintenance Period, subjects whose dose has been down-titrated can have their dose increased again, as soon as tolerability improves. This can be done at an unscheduled clinic visit or at the next clinic visit after the investigator has deemed it appropriate based on the resolution of AE(s).

Subjects who complete the Maintenance Period will have the option to roll over into Extension A and will immediately begin the blinded Conversion Period.

Subjects who do not continue in Extension A or those who prematurely discontinue from the study will return to the study site for Follow-up visits 1 week and 4 weeks after the last study drug administration. (revised per Amendment 04)

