9.4 TREATMENTS

9.4.1 Treatments Administered

The following treatments will be administered during the Randomization Phase:

- Perampanel: single daily dose of perampanel oral 2-mg tablets with multiple tablets dispensed to give a dose of 2 mg/day to 8 mg/day. (revised per Amendment 04)
- Perampanel: single daily dose of perampanel oral suspension 0.5 mg/mL, with the volume dispensed adjusted to give a dose of 2 mg/day to 8 mg/day. (revised per Amendment 04)
- Placebo matched to perampanel 2-mg tablets
- Placebo matched to perampanel oral suspension

It is recommended that oral tablet be used for dosing subjects ≥ 12 years of age and oral suspension be used for subjects < 12 years of age (at the time of signing informed consent); however, the most appropriate formulation may be selected based on the subject's condition and at the discretion of the investigator. The same formulation should be used for a given subject throughout the course of the study. Dosing should occur orally once a day before bedtime. Before the PK sampling visits, the dosing date and time of the previous 3 doses before each PK sampling visit will be recorded. Study drug administration in the evening immediately before (and the evening on the day of) Visit 5 and Visit 6 should be withheld (all other AEDs should be administered per the subject's usual AED regimen). Study drug will be given during Visit 5 and Visit 6 at the study site (within 1 to 5 hours after dose administration). Bedtime will resume in the evening on the day of Visit 5 and Visit 6. (revised per Amendment 04)

The subject will continue to take their baseline anti-epileptic medication regimen throughout the Randomization Phase. Changes of baseline AEDs (addition, deletion, or adjustment in dose) are not allowed during the Randomization Phase. (revised per Amendment 01)

The following treatments will be administered to subjects in this study (Table 1). The dosage form administered at the start of the Titration Period (tablets or suspension [ie, the most appropriate formulation selected based on the subject's condition and at the discretion of the investigator]) will be continued throughout the study (Core and Extension) even if a subject reaches 12 years of age during this time. (revised per amendment 04)

Table 1 Dosage Schedule in E2007-G000-338 (Randomization Phase Core Study)

| Randomization Phase/ Titration Period | Visit | All Subjects |
|---|---|--------------|
| Week 1 (starting dose) | Visit 2 | 2 mg/day |

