| Week 2 | Visit 3 | 4 mg/day |
| Week 3 | - | 6 mg/day |
| Week 4 | Visit 4 | 6 mg/day |
| Week 5 ^a | - | 8 mg/day |
| Week 6 ^a | - | 8 mg/day |
| Randomization Phase/ Maintenance Period (Week 7/Visit 5)^b | Starts the Maintenance Period at the last dose achieved in the Titration Period | |

a: Subjects will remain on dose for at least 2 weeks before entering the Maintenance Period.

b: Dosing should occur orally once a day before bedtime, except on the evenings immediately before (and the evening on the day of) Visit 5 and Visit 6. Study drug administration in the evening immediately before (and the evening on the day of) Visit 5 and Visit 6 should be withheld (all other AEDs should be administered per the subject's usual AED regimen). Study drug will be given during Visit 5 and Visit 6 at the study site, after collection of predose PK sample (within 1 to 5 hours after dose administration). Bedtime dosing will resume in the evening on the day of Visit 5 and Visit 6. (revised per Amendment 04)

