| Week 19 (starting dose) | Visit 7 | 2 mg/day |
| Week 20 | -- | 4 mg/day |
| Week 21 | Visit 8 | 6 mg/day |
| Week 22 | -- | 6 mg/day |
| Week 23 ^a | Visit 9 | 8 mg/day |
| Week 24 | -- | 8 mg/day |
| Extension A/ Open-label Maintenance Period (beginning Week 25) | Visit 10 | Starts Extension A Maintenance Period at the last dose achieved in the Conversion Period ^b |

- a. Subjects will remain on the same dose for at least 2 weeks before entering the Open-label Maintenance Period.
- b. After the double-blind Conversion Period, subjects can be titrated up to 12 mg/day (except in Japan, where the maximum allowed dose remains at 8 mg/day), in 2-week intervals as per the investigator's discretion.

Per the investigators' judgment, all subjects will be allowed to have their dose decreased only if they experience intolerance, or their dose increased only if needed for better seizure control until the optimal dose is found. Subjects whose dose has been decreased can have their dose increased again, as soon as tolerability improves. Dose decreases can be done at an unscheduled clinic visit or via telephone.

After the double-blind Conversion Period, subjects can be titrated up to 12 mg/day (except in Japan where the maximum allowed dose remains at 8 mg/day), in 2-week intervals as per the investigator's discretion.

All dose adjustments during this phase will be done by going one dose level up or down. Subjects who do not tolerate a daily dose of 2 mg will be discontinued from the study.

Down-titration of perampanel upon early discontinuation or completion of the study is not necessary, because the plasma half-life of perampanel is between ~25 to 105 hours. As such, plasma concentrations decrease gradually following stopping perampanel. If, in the clinical judgment of the investigator, down-titration of perampanel is still deemed necessary, the investigator must discuss the down-titration before the early discontinuation (or at the end of Extension A) with the Medical Monitor.

During Extension A, changes of concomitant AEDs (addition, deletion or adjustment in dose) will be allowed. However, if changes do occur subjects should be carefully monitored.

EXTENSION A ASSESSMENTS

Seizure diaries will be used to collect seizure counts and types.

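### Dosing at Visits 5 and 6: five places both withhold and resume the bedtime dose on the same evening, and omit the condition under which withholding applies

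*Protocol*

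**What the plan says.** Six places in the current protocol, all revised under Amendment 04, give dosing instructions around the PK sampling at Visits 5 and 6.

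The note under Study Treatments in the synopsis is conditional. It applies "if due to infeasibility of PK sample collection before and after evening/bedtime dose administration, then the following steps are to be followed". In that case study drug "in the evening immediately before Visit 5 and Visit 6 should be withheld", the predose sample is taken, drug is given on site, a second sample follows 1 to 5 hours later, and bedtime dosing resumes that evening.

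The other five places read differently. Section 9.1.2.2 says "Study drug administration in the evening immediately before (and the evening on the day of) Visit 5 and Visit 6 should be withheld", followed by "Bedtime dosing will resume in the evening on the day of Visit 5 and Visit 6". Section 9.4.1 repeats the withholding sentence and then says "Bedtime will resume in the evening on the day of Visit 5 and Visit 6", with the word for dosing missing. Table 5 footnote r repeats the pair. Footnote b to the synopsis dosage table and footnote b to Table 1 go further. Besides the withholding sentence, they list the visit-day evening as an exception to bedtime dosing ("except on the evenings immediately before (and the evening on the day of) Visits 5 and 6" and "except on the evenings immediately before (and the evening on the day of) Visit 5 and Visit 6"), and then resume bedtime dosing on that evening.

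**The concern.** For the evening of the visit day, the five places give opposite orders. A site must choose, and sites may choose differently. At the target dose the choice is between 8 and 16 mg on one calendar day, in a blinded trial that enrols from age 2 and from 8 kg.

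Two further consequences follow. Withholding has become the rule even where sampling around the bedtime dose is feasible, so doses are moved without need. Also, Section 9.5.4.3 defines overdose as use above the dose the protocol sets, and routes associated adverse events through the serious-event procedure. With the visit-day dose undefined, sites cannot classify a second dose consistently.

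**Working it through.** **Text comparison**

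| Place | Evening before | Visit-day evening withheld? | Bedtime dosing resumes visit-day evening? | Infeasibility condition? |
|---|---|---|---|---|
| Synopsis, Study Treatments note | withheld | no | yes | yes |
| Synopsis dosage table, footnote b | withheld | yes (stated twice) | yes | no |
| Section 9.1.2.2 | withheld | yes | yes | no |
| Section 9.4.1 | withheld | yes | yes | no |
| Table 1, footnote b | withheld | yes (stated twice) | yes | no |
| Table 5, footnote r | withheld | yes | yes | no |

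The parenthesis about the visit-day evening occurs 2 + 1 + 1 + 2 + 1 = 7 times. Two possible reconciliations fail:

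- Resuming cannot mean the following evening, because every place names the evening of the visit day.
- The on-site dose is not the resumed bedtime dose, because it is described separately. Where the sampling step is kept, it follows the predose sample.

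Section 9.1.2.2 still refers back to certain cases when it asks for the previous three dose times, but no cases are defined there. That suggests the condition was lost in drafting.

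**Doses over the evening before plus the visit day, at 8 mg**

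- Usual regimen: 1 + 1 = 2 doses, 16 mg.
- Two-dose reading: 0 + on-site + bedtime = 2 doses, 16 mg, both on the visit day.
- One-dose reading: 0 + on-site = 1 dose, 8 mg.

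The two-dose reading restores the usual two-day total; the one-dose reading loses a dose.

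**Exposure**

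The half-life is from Appendix 2, which says down-titration is unnecessary "because the plasma half-life of perampanel is between ~25 to 105 hours". The rest is assumed: one compartment, instantaneous absorption, steady state on 8 mg every 24 h, and an on-site dose *v* = 10 to 18 h after the withheld evening dose. Amounts are in mg-equivalents. With f(t) = 2^(−t/half-life):

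- usual peak P = 8 / (1 − f(24)); usual trough T = P × f(24)
- two-dose peak, after the visit-day bedtime dose = T × f(24) + 8 × f(24 − v) + 8
- one-dose trough, before the next bedtime dose = T × f(48) + 8 × f(48 − v)

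Worked case, half-life 25 h and v = 10 h: f(24) = 0.514, P = 16.46, T = 8.46.

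- Two-dose peak = 4.35 + 5.43 + 8 = 17.78, which is 8.0% above P.
- One-dose trough = 2.24 + 2.79 = 5.03, which is 40.6% below T.

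| Half-life | P | T | Two-dose peak, v = 10 / 12 / 18 h | One-dose trough, v = 10 / 12 / 18 h |
|---|---|---|---|---|
| 25 h | 16.46 | 8.46 | +8.0% / +9.9% / +16.2% | −40.6% / −38.7% / −32.4% |
| 105 h | 54.60 | 46.60 | +0.9% / +1.0% / +1.6% | −13.8% / −13.6% / −13.1% |

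The model is linear, so the percentages are the same at lower dose levels.

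**Reach**

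- Subject-visits: 142 randomised 1:1 gives 71 on perampanel, and 71 x 2 visits = 142. This is an upper limit. Subjects who passed these visits before Amendment 04 (19 Oct 2018, against a planned start of about Jan 2017), or who left earlier, were not exposed to the wording. The documents do not give the true number.
- Compliance: 18 weeks x 7 = 126 planned doses. At most 2 are lost, and 2/126 = 1.6%, against the 80% cut-off in the SAP's protocol deviations section.
- PK: if the visit is in the daytime, both samples come before the disputed dose.

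**The case against.** The contradiction itself is not in dispute. The arguments on the other side concern which instruction is wrong and how much it matters.

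**Intent.** The visit-day evening is withheld in five of the six places. The one-dose reading also fits the once-daily regimen and the Core Study maximum of 8 mg/day (Sections 9.1.2.1, 9.4.1 and 9.4.4). Deleting the parenthesis would make 16 mg on one day the rule in the infeasible case. This stands as a reason to have the clinical team confirm intent before the text is changed. Against it, all six places say bedtime dosing resumes on the visit evening, and the only coherent version is the one that gives two doses.

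**Size.** The largest effects need the 25 h half-life; at 105 h they are under 2% for the peak and about 14% for the trough. Dose times before each sampling visit are recorded. This is right, and the effect on trial results is small. It does not make the instruction workable.

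**Cost.** Section 11.1 requires a written amendment or administrative change, so a letter to sites alone may not be enough. This stands, as a minor point.

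**Timing.** The Core SAP describes the PK samples as already drawn, and the Extension SAP refers to early termination. If Visits 5 and 6 are complete, a correction can only serve the record.

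**Conclusion.** The concern holds. Current protocol text in five places gives a dosing instruction that cannot be followed, and those places omit the condition that limits when withholding applies. Because one of them is the synopsis dosage table, the synopsis also contradicts its own note.

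The two readings differ by one dose per visit, 8 against 16 mg on the visit day at the target dose, for at most 142 perampanel subject-visits. The exposure range (peak up by about 1% to 16%, or trough down by about 13% to 41%) rests on the assumed one-compartment model and the 10 to 18 h dosing gap. The textual finding rests on no assumption. The point should be corrected for dosing safety and consistency between sites. It does not threaten the efficacy, PK or compliance analyses, and no sample size or power figure depends on it.

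**What to change.** 1. Have the clinical team confirm that an on-site dose plus a bedtime dose on the visit day is intended when sampling around the bedtime dose is infeasible.
2. If so, delete the parenthesis about the visit-day evening at all seven occurrences: two each in footnote b of the synopsis dosage table and of Table 1, and one each in Section 9.1.2.2, Section 9.4.1 and Table 5 footnote r.
3. Restore the infeasibility condition in those five places, using the steps in the synopsis note with its grammar corrected.
4. In the same edit, supply the missing word in Section 9.4.1. Where the 1-to-5-hour window is attached to giving the drug, attach it to the postdose sample.

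If the team instead intends a single dose on the visit day, the resumption sentence must be changed in all six places.

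The cost is a wording correction, issued as an amendment or administrative change under Section 11.1, with notice to sites. Sample size, endpoints and the SAP are unaffected.

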9.1.2.3 Follow-up Period

Subjects who do not continue in Extension A or those who prematurely discontinue from the study will return to the study site for Follow-up visits 1 week and 4 weeks after the last study drug administration. At the end of the 4-week Follow-up Period, subjects will return to study site to complete the End-of-Study assessments (Follow-Up visit). These assessments will also be performed if a subject prematurely discontinues from the study, after the Early Discontinuation Visit. (revised per Amendment 04)

9.1.3 Extension A

A subject who completes the Maintenance Period of the Core Study will be eligible to enter Extension A, which consists of 3 periods: Conversion Period (6 weeks), Maintenance Period (46 weeks), and Follow-up (4 weeks; only for those subjects not entering into Extension B). The total treatment duration in Extension A is 52 weeks for evaluation of long term safety and efficacy. (revised per Amendment 04)

Subjects will immediately begin the blinded Conversion Period starting at Week 19. During the Conversion Period, subjects who received perampanel during the Core Study will continue receiving perampanel in a blinded manner at the same dose received during the Core Maintenance Period. Subjects who received placebo during the Core Study will begin treatment with perampanel in a blinded manner, following the same dosing regimen and titration schedule as that in the Core Study, starting at 2 mg/day and will then be up-titrated as described above for the Core Study, to the optimal dose per the investigator's discretion, not to exceed a maximum dose of 8 mg/day. After the double-blind Conversion Period, subjects can be titrated up to 12 mg/day (except in Japan, where the maximum allowed dose remains at 8 mg/day), in 2-week intervals during the Extension A Maintenance Period as per the investigator's discretion. The total treatment duration in Extension A is 52 weeks for evaluation of long term safety and efficacy. Addition, deletion, and dose changes to the concomitant AEDs are allowed during Extension Maintenance Period. (revised per Amendment 04)

After completion of Extension A, an additional Extension Phase (Extension B) with open-label treatment will be available for optional participation to subjects who reside in Japan or subjects in countries where an extended access program (EAP) cannot be implemented or has not yet been implemented, and who in the opinion of the investigator continue to benefit from treatment with perampanel. All subjects, except for those entering Extension B, will enter a 4-week Follow-up Period, which will have 1 visit during which End-of-Study assessments will be performed. (revised per Amendment 04)

Further information regarding Extension A is provided in [Appendix 2](#).

